11.3.3 Survival follow-up

The survival follow-up period starts after the end of the safety follow-up period. The survival follow-up period ends upon the subject's death, lost to follow-up, withdrawal of informed consent, or study termination by sponsor. During this period, an effective follow-up such as telephone follow-up will be conducted once every 2 months to collect information on subject survival and subsequent treatments (if the subject has started a new anti-tumor treatment, the therapeutic regimen and the start and end time should be recorded).

11.4 Criteria for Crossover Treatment of Control Group

Subjects who are willing to and eligible for crossover treatment may be crossed over to receive the treatment of SHR-1210 combined with apatinib.

11.4.1 Screening Period

Unless otherwise stated, the following procedures must be completed within 7 days prior to the start of study treatment during at the screening visit (Day-7 to Day-1):

- Obtain informed consent form signed by the subject.
- Virology: HBsAg (quantitative HBV DNA test if positive); HCV-Ab (quantitative HCV-RNA test if positive) and HIV-Ab: within 28 days before the first dose.
- Echocardiography: Including left ventricular ejection fraction (LVEF) assessment. Echocardiography will be performed once within 28 days prior to the first dose, and performed if clinically indicated thereafter.
- Imaging evaluation: CT or MRI of lesions in the head, chest, abdomen, pelvis, and other sites. Sites with bone metastasis as shown by bone scans, PET-CT, or clinical indications must also be reexamined by CT or MRI at baseline but no longer undergo bone scan or PET-CT for efficacy follow-up.
- Collection of adverse events: Collect adverse events starting from the signing of ICF.
- Concomitant medications/treatments: Concomitant medications/treatments within 28 days prior to the first dose of the study drug should be documented.
- ECOG PS.
- Vital signs: pulse, respiratory rate, temperature, and blood pressure.
- Comprehensive physical examination: height, weight, general condition, head and face, neck, chest, abdomen, perineum, extremities, etc.

- Hematology: Red blood cell count (RBC), hemoglobin (Hb), blood platelet count (PLT), white blood cell count (WBC), absolute neutrophil count (ANC), and lymphocyte count (LYM).
- Urinalysis: WBC, RBC, and urine protein. If urine protein is $\geq 2+$, then a quantitative 24-h urine protein test should be added.
- Fecal occult blood (OB): within 7 days before the first dose.
- Blood biochemistry: Alanine transaminase (ALT), aspartate aminotransferase (AST), gamma-glutamyl transferase (γ -GT), total bilirubin (TBIL), direct bilirubin (DBIL), alkaline phosphatase (AKP), blood urea nitrogen (BUN) or urea, total protein (TP), albumin (ALB), creatinine (Cr), blood glucose (GLU), serum potassium (K $^{+}$), serum sodium (Na $^{+}$), serum calcium (Ca $^{2+}$), serum magnesium (Mg $^{2+}$), and blood chloride (Cl $^{-}$).
- Coagulation function: Activated partial thromboplastin time (APTT), prothrombin time (PT), thrombin time (TT), fibrinogen (FIB), and international normalized ratio (INR).
- Thyroid function: Including serum thyroid stimulating hormone (TSH), free triiodothyronine (FT3), and free thyroxine (FT4). If FT3 and FT4 cannot be obtained, T3 and T4 are allowed for substitution;
- 12-Lead ECG: Attention should be paid to heart rate, QT, QTcF, and P-R intervals. The investigator may decide to add other investigations if the results are abnormal.
- Echocardiography
- Pregnancy test (serum pregnancy test will be performed for women of childbearing potential).
- Quality of life score.

11.4.2 Treatment period

The content of the visit is the same as [11.2.1 Treatment period for the investigational treatment group](#).

11.4.3 Follow-up period

The content of the visit is the same as [11.3.1 Safety follow-up for the investigational treatment group](#).

11.5 Unscheduled Visit

The following shall be documented during unscheduled visits when subjects develop AEs during the study:

- Concomitant medications/treatments;
- Adverse events;
- All examinations performed related to adverse events (including radiographic examinations, if any).

12 EVALUATIONS

12.1 Efficacy Evaluation

In addition to the investigator's assessments of the tumor imaging results in this study, the sponsor will also collect all imaging results (except for the imaging results of the control group after crossover treatment), and use them for blinded independent review (all per RECIST v1.1). The specific procedures for independent review are described in the "Third-Party Independent Review Charter" for this study, written by the central imaging.

PFS: the time between the date of enrollment and the date of the first documented tumor progression (as per RECIST v1.1, regardless of whether treatment is continued), or death from any cause, whichever occurs first.

In addition, subjects in the investigational treatment group will continue the study treatment after progressive disease. The investigator will perform subsequent imaging assessments as per iRECIST (see Appendix 11; independent imaging evaluation is still carried out as per RECIST v1.1) for exploratory evaluation of PFS in the investigational treatment group as per iRECIST. PFS is defined as the period of time from the date of the subject's enrollment to the first iUPD that can be subsequently confirmed or the date of death due to any cause, whichever occurs first. The imaging evaluation criteria of the control group after crossover treatment are the same as those of the investigational treatment group, but no independent review of central imaging will be performed. The subjects after crossover will be analyzed based on the PFS data as per RECIST v1.1 and iRECIST.

OS: the time from the date of enrollment to the date of death from any cause. Subjects whose final status is "survived" are censored, and the date of censoring is the date of the last follow-up.

ORR: the proportion of treated subjects whose best overall response (BoR) is complete response (CR) or partial response (PR) as per RECIST1.1.

DCR: the proportion of treated subjects whose best overall response is complete response (CR), partial response (PR), or stable disease (SD) as per RECIST v1.1.

DoR: the period of time from the first documented tumor response (as per RECIST v1.1) to the first documented objective progression (as per RECIST v1.1) or death of any cause.

iORR: the proportion of treated subjects whose best overall response (BoR) is complete response (CR) or partial response (BOR) as per iRECIST v1.1.

iDCR: the proportion of treated subjects whose best overall response is complete response (CR), partial response (PR), or stable disease (SD) as per iRECIST v1.1.

iDoR: the period of time from the first documented tumor response (as per iRECIST v1.1) to the date of the first iUPD that can be subsequently confirmed or the date of death from any cause.

12.2 Safety Evaluation

12.2.1 Pregnancy test

Female subjects of childbearing potential will receive a sub-serum pregnancy test before the start of administration. When the pregnancy test shows negative during the screening period, appropriate contraceptive measures shall be taken.

Pregnancy test will also be performed routinely once every two cycles during the treatment period and at the end of study treatment, or additionally when a menstrual cycle is missed or when signs of pregnancy are suspected. If the HCG test is positive, the subject discontinues the dose but will continue to be observed for follow-up of the pregnancy event.

12.2.2 Adverse event

The evaluation of an adverse event (AE) includes the type, incidence, severity (according to NCI-CTCAE v4.03), and start and end time of the AE, as well as whether the AE is a SAE, the correlation of the AE to the study drug, and the outcome of the AE.

AEs that occur during the study, including signs and symptoms at screening, will be recorded on the AE page of the CRF.

12.2.3 Laboratory safety assessment

The blood samples for hematology and blood biochemistry tests will be collected according to the Schedule of Activities, and will be analyzed at the local laboratory.

Table 9. Laboratory tests

Hematology	Blood biochemistry	Serum sodium	FT4 (or T4)
Red blood cell	ALT	Serum calcium	Myocardial zymogram
Hemoglobin	AST	Serum magnesium	Lactate dehydrogenase
Blood platelet	Glutamyl transpeptidase	Blood chlorine	Creatine kinase
White blood cell	Total bilirubin	Coagulation function	Hybrid creatine kinase
Absolute neutrophil count	Direct bilirubin	APTT	Pregnancy Test
Lymphocyte count	Alkaline phosphatase	PT	Serum pregnancy test
Urinalysis	Blood urea nitrogen (or urea)	TT	
White blood cell	Total protein	FIB	
Red blood cell	Albumin	INR	
Urine protein	Creatinine	Thyroid function	
Fecal occult blood	Glucose	TSH	
Occult blood	Serum potassium	FT3 (or T3)	

12.2.4 Vital signs and physical examination

Physical examinations and vital sign examinations are completed by the research physician.

Vital signs include temperature, blood pressure, pulse, and respiratory rate.

Physical examination: height, weight, general condition, head and neck, chest, abdomen, perineum, and extremities. Height will be measured during screening only.

12.2.5 12-Lead electrocardiography (ECG)

12-Lead ECG shall be performed at the time points specified in the "Schedule of Activities".

Subjects are required to rest quietly for at least 10 minutes in a supine position prior to undergoing the ECG. The ECG includes at least: heart rate, QT, and P-R intervals. QTcF can be calculated as: $QTcF = QT/(60/\text{heart rate})^{0.33}$.

12.2.6 Echocardiography

Echocardiography will be performed by qualified physicians. LVEF is also measured.

12.3 Collection and Processing of Immunogenicity and Drug Trough Concentration Blood Samples

Peripheral blood of subjects receiving SHR-1210 combined with apatinib will be used for immunogenicity and PK concentration testing. Refer to the "Laboratory Manual" for details.

12.4 Independent Data Monitoring Committee

In this study, an Independent Data Monitoring Committee (IDMC) will be established to evaluate the safety and efficacy of the study drug at the data review meetings on a regular basis. An interim analysis will be performed when about 143 (67%) OS events will be collected. The IDMC will make recommendations on whether to continue or terminate the study based on the safety and efficacy data and results. The IDMC review meeting will be held at the time specified in the charter of the IDMC. The study enrollment will continue during IDMC meetings.

After the data review, the IDMC will provide suggestions on whether to continue the study, whether to modify the protocol, or whether to discontinue the study. Finally, Jiangsu Hengrui Pharmaceuticals Co., Ltd. will decide whether to adopt the IDMC suggestions.

See details in IDMC charter.

13 ADVERSE EVENTS REPORTING

13.1 Adverse Events (AEs)

13.1.1 Definition of adverse event

An AE refers to any untoward medical condition in a clinical study subject who receives a pharmaceutical product, and the condition does not necessarily have a causality with the treatment. AEs can include any unfavorable and unintended symptoms, signs, abnormal laboratory finding, or diseases, including the following:

- 1) Worsening of pre-existing (prior to entering clinical study) medical conditions/diseases (including worsening symptoms, signs, or laboratory abnormalities);
- 2) Any new AE: Any new adverse medical conditions (including symptoms, signs, and newly diagnosed diseases);
- 3) Clinically significant abnormal laboratory findings.

All AEs should be collected in detail by the investigators, including: the name of the AE and description of all relevant symptoms, onset time, severity, causality assessment, duration, measures taken, as well as final results and outcomes.

13.1.2 AE severity grading criteria

The severity of AEs will be graded as per NCI-CTCAE v4.03. Refer to the following criteria for AEs not listed in the table of NCI CTCAE v4.03:

Table 10. CTC-AE severity grading criteria

Grade	Clinical Description of Severity
1	Mild; asymptomatic or mild clinical symptoms; clinical or laboratory test abnormality only; intervention not indicated.
2	Moderate; minimal, local, or noninvasive intervention indicated; limiting age-appropriate instrumental activities of daily life, e.g., cooking, shopping, using the telephone, counting money, etc.
3	Severe or medically significant but not immediately life-threatening; leading to hospitalization or prolongation of hospitalization indicated; disabling; limiting self-care activities of daily living (ADL). Self-care ADL: refer to bathing, dressing and undressing, feeding self, using the toilet, taking medications, and not bedridden
4	Life-threatening consequences; urgent intervention indicated
5	Resulting in death

13.1.3 Determination of the relationship between AEs and the study drug

AEs include all unexpected clinical manifestations. All AEs that occur after the signing of the ICF must be reported regardless of whether the AEs are related to the study drug, whether the subject is allocated to the treatment group, and whether the subject receives the drug. Any discomforts complained by the subject or changes in objective laboratory measurements during the treatment period should be truthfully recorded. The severity, duration, measures taken, and the outcome of AEs should also be documented. The study physician shall assess the relationship between the AE and the study drugs by considering the time sequence between the administration of study drug and the occurrence of AE, characteristics and toxicology of the study drug, concomitant medications, underlying diseases, medical history, family history, as well as dechallenge and rechallenge. The causality assessment will be provided using the following five categories "definitely related, possibly related, unlikely related, definitely unrelated, and indeterminable". "Indeterminable" to be adverse drug reaction.

13.2 Serious Adverse Event (SAE)

13.2.1 Definition of SAE

A SAE refers to a medical occurrence during the study that results in hospitalization, prolonged hospitalization, disability, incapacity, life-threatening or death, or congenital malformation.

The following medical events are included:

- Events resulting in death;
- Life-threatening events (defined as when the subject is at immediate risk of death at the time of the event);
- Events resulting in hospitalization or prolonged hospitalization;

- Events resulting in permanent or serious disability/incapacity/impairment of work ability;
- Congenital anomalies or birth defects;
- Other important medical events (defined as events that may jeopardize the subject or require interventions to prevent any of the above).

13.2.2 Hospitalization

AEs resulting in hospitalization (even if for less than 24 hours) or prolonged hospitalization during the clinical study should be considered as SAEs.

Hospitalization does not include the following:

- Hospitalization at a rehabilitation institution
- Hospitalization at a sanatorium
- General emergency admission
- Day surgery (e.g., outpatient/same-day/ambulatory surgery)
- Social reasons (medical insurance reimbursement, etc.)

Hospitalization or prolonged hospitalization unrelated to the worsening of an AE is not a SAE. For example:

- Hospitalization due to the pre-existing disease without new AEs and aggravation of the pre-existing disease (e.g., hospitalization to examine laboratory abnormalities that have persisted from before the study until now);
- Hospitalization for management reasons (e.g., annual physical examination);
- Hospitalization during the study as specified in the study protocol (e.g., as required by the protocol);
- Elective hospitalization unrelated to worsening of AEs (e.g., elective surgery);
- Scheduled treatment or surgery that should be documented throughout the entire study protocol and/or in the subjects' individual baseline information;
- Hospitalization merely for use of blood products.

Diagnostic or therapeutic invasive (e.g., surgery) and non-invasive procedures should not be reported as AEs. However, when a condition resulting in such procedures meets the definition of AE, it should be reported as such. For example, acute appendicitis during the AE reporting period should be reported as an AE, and the resulting appendectomy shall be recorded as the treatment of the AE.

13.2.3 Progressive disease

Progressive disease is defined as the worsening of the subject's conditions caused by the indications of the study, including radiological progressions and progressions in clinical symptoms and signs. New metastases relative to the primary tumor or progressions of the previous metastases are recognized as PD. Life-threatening events, hospitalization or prolonged hospitalization, or events resulting in permanent or severe disability/incapacity/impairment of work ability, congenital anomalies or birth defects arising from the symptoms and signs of PD are not reported as SAEs. Death caused by the symptoms and signs of PD will be reported as a SAE.

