In this study, the screening period should be no more than 28 days. After completing screening examinations and assessments, eligible subjects will enter the treatment period and receive the study treatment and study visits according to the protocol. Among them, tumor imaging assessment will be performed once in every 2 cycles during the first 16 cycles and once every 4 cycles thereafter. The independent review committee (IRC) will review the imaging evaluation results of each study center. The safety follow-up period of subjects in the investigational treatment group starts after the last dose, and the subjects will be followed up once every 30 days until 90 days after the last dose. Among them, the first safety follow-up will be carried out at the study center; the second and the third follow-up visits will be made via phone calls. For subjects in the control group, if they do not receive SHR-1210 + apatinib treatment, their safety follow-up period will be 21 days after the last dose; otherwise, the same arrangement as that in the investigational treatment group will be used. The survival follow-up period will start after the end of the safety follow-up period. The survival follow-up period will end upon the subject's death, lost to follow-up, withdrawal of informed consent, or study termination by the sponsor. During this period, a follow-up shall be conducted every 2 months via phone calls or other effective methods to collect information on subject survival and subsequent anti-tumor treatment.

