13.2.5 SAE reporting

In the event of a SAE, whether it is the first report or a follow-up report, the investigator must complete the "Serious Adverse Event Report Form" immediately, with a signature and date, and notify the sponsor within 24 h of knowing of the event. Relevant authorities must be informed of such SAE in a timely manner according to regulatory requirements.

SAEs that occur after the safety follow-up period which are suspected to be related to the study drugs should be collected.

The symptoms, severity, causality with the study drug, time of onset, time of treatment, measures taken, time and method of follow-up, and outcome should be documented in detail in the SAE report. If the investigator believes that a SAE is not related to the investigational drug but potentially related to study conditions (such as the termination of the previous treatment, or comorbidities during the study), this causality should be explained in the description section of the SAE report form. If the severity of an ongoing SAE or its relationship to the study drug changes, a follow-up report should be submitted immediately. If an error is found in a previously reported SAE, such SAE may be revised, revoked, or downgraded in follow-up reports and reported in accordance with the SAE reporting procedure.

The sponsor's email address for safety data of this study is: [contact]

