13.2.6 Time limit for collection and follow-up of AEs/SAEs

All AEs/SAEs will be collected from the signing of the informed consent form. The time limit and follow-up periods for new events are described in the table below.

Table 11. Principles of AE/SAE collection and follow-up

Classification	Onset Time	Follow-up Time
Unrelated AEs	Until the end of safety follow-up period or start of a new anti-tumor treatment (whichever comes first)	Until the end of safety follow-up period
Treatment-related AEs	Until the end of safety follow-up period	Until resolved, remission, or recovered to baseline levels or Grade ≤ 1 , steady state, or reasonably explained (e.g., lost to follow-up, death).
Unrelated SAEs (including SIEs)	Until the end of safety follow-up period or start of a new anti-tumor treatment (whichever comes first)	Until the end of safety follow-up period
Treatment-related SAEs (including SIEs)	No time limit	Until resolved, remission, or recovered to baseline levels or Grade ≤ 1 , steady state, or reasonably explained (e.g., lost to follow-up, death).

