5.5 Safety Analysis

All safety analyses will be conducted based on SS. All safety analyses will be presented by treatment group.

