5.5.2 Adverse event

AEs will be classified by treatment stage (before and after study treatment).

All AEs will be coded with MedDRA (version, 23.1). and graded using NCI-CTCAE v4.03. For the same SOC and/or PT, multiple cases of the same events that occur in one subject will be counted only once. For the same AE reported in one subject multiple times but varying in CTCAE grade, the AE of the greatest grade will be enumerated.

AEs will be sorted by incidence from high to low based on SOC, and PT under each SOC. If the incidence of ≥ 2 PT is equal, the AEs will be sorted alphabetically. If there is no AE under a SOC or PT, then analysis will not be conducted.

A treatment-emergent adverse event (TEAE) is defined as any adverse event that occurs after the start of study treatment. Only TEAEs will be summarized. All AEs will be listed. AEs with completely missing onset time will be treated as TEAEs.

For AEs occurring after the start of study treatment, treatment-related AEs include those whose causality with the study drug is definitely related, possibly related, or indeterminable; if the causality assessment is missing, then the AE will be deemed treatment-related for analysis.

In a listing of AEs, TEAEs will be analyzed by group, and frequencies and proportions will be statistically described. AEs will be summarized using descriptive statistics according to Hengrui's Statistical Analysis Reporting Standards, including but not limited to the following contents:

- Any TEAE
- Treatment-related AEs (TRAEs)
- Any TESAE
- Treatment-related SAEs (TRSAEs)
- Any SAE
- Any drug-related SAE
- TEAEs resulting in dose reduction, dose interruption followed by reduction, interruption, or treatment discontinuation
- TRAEs resulting in dose reduction, dose interruption followed by reduction, interruption, or treatment discontinuation
- TEAEs resulting in death
- Immune-related adverse events ("reactive capillary endothelial proliferation" will all be considered immune-related events)?
- Was hormone therapy used?

The incidence of AE is calculated based on the number of subjects having an AE, instead of the number of AE episodes.

All AEs will be listed. Drug-related AEs, AEs resulting in treatment discontinuation, AEs resulting in dose reduction or dose interruption followed by reduction or treatment interruption, and death will be listed.

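### The all-cause SAE and fatal-TEAE rows in SAP 5.5.2 count progression deaths and other unrelated SAEs over unequal post-treatment windows (nominally 90 days against 21), and no common-window or PD-excluded version is named

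*Protocol*

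**What the plan says.** **What counts as an SAE.** Protocol 13.2.3 keeps most serious consequences of progression out of SAE reporting but makes an exception for death: "Death caused by the symptoms and signs of PD will be reported as a SAE".

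**How long unrelated SAEs are collected.** Table 11 (Protocol 13.2.6) sets the onset limit: "Until the end of safety follow-up period or start of a new anti-tumor treatment (whichever comes first"). Treatment-related SAEs have no limit, and 13.2.5 agrees: "SAEs that occur after the safety follow-up period which are suspected to be related to the study drugs should be collected".

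**How long safety follow-up lasts.** In the investigational arm, Protocol 7.1 says "the subjects will be followed up once every 30 days until 90 days after the last dose". Controls who do not cross over have 21 days after last dose. Controls who do cross over follow the investigational scheme. The synopsis and SAP 2.1 say the same. Visits carry a window of ±5 days.

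**What is tabulated.** SAP 5.5.2: "A treatment-emergent adverse event (TEAE) is defined as any adverse event that occurs after the start of study treatment". No end date is given. The rows listed include Any TESAE, Any SAE and "TEAEs resulting in death", together with treatment-related and drug-related SAE rows. The list follows the sponsor's reporting standards and is introduced as "including but not limited to the following contents". SAP 5.5 adds: "All safety analyses will be presented by treatment group".

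**After crossover.** Protocol 14.4.9 plans a separate descriptive safety summary for crossed-over controls, and SAP 2.2.3 lists it as an exploratory objective. Neither says whether those events also count in the control column of the main tables.

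**The concern.** Comparing safety between arms is a secondary objective (Protocol 6.1.2), and the incidence of AEs and SAEs is a secondary endpoint (6.2.2). The three all-cause rows place the arms side by side although unrelated events, including deaths from sarcoma, are collected for longer after treatment in one arm than in the other. Two regimens with the same toxicity and the same survival could then show different counts of SAEs and fatal events. A reader of the table could take an artefact of follow-up for a difference in safety, most probably to the disadvantage of the investigational regimen.

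**Working it through.** **1. The rules together.** A death from PD after last dose is an SAE (13.2.3). If it is judged unrelated, it is collected only while safety follow-up is open and no new therapy has begun (Table 11). If collected, it meets the TEAE definition and enters all three all-cause rows. The nominal windows stand in the ratio 90/21 = 4.3.

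**2. Plan's own figure.** There is none to reproduce. The documents give no rate of death after last dose and no rate of starting new therapy. What follows is an illustration on assumed values.

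**3. Formula.** Take the same constant death hazard after last dose in both arms, λ = ln 2 / (median survival after last dose), and a competing hazard of new therapy, μ = ln 2 / (median time to new therapy), with μ = 0 if none starts. Treat all these deaths as due to PD and judged unrelated. The probability that a death is captured within d days is

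P(d) = λ/(λ+μ) × [1 − exp(−(λ+μ) × d/30.4375)].

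Example with a 12-month median and no new therapy: λ = 0.0578 per month. P(90) = 1 − exp(−0.0578 × 2.957) = 15.7%. P(21) = 1 − exp(−0.0578 × 0.690) = 3.9%.

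**4. Results** (percent of subjects leaving treatment)

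| Median survival after last dose | Median time to new therapy | P(90) | P(21) | Ratio |
|---|---|---|---|---|
| 4 months | none starts | 40.1 | 11.3 | 3.56 |
| 4 months | 3 months | 29.9 | 10.4 | 2.87 |
| 4 months | 1.5 months | 23.1 | 9.7 | 2.39 |
| 6 months | none starts | 28.9 | 7.7 | 3.78 |
| 6 months | 3 months | 21.4 | 7.1 | 3.01 |
| 6 months | 1.5 months | 16.4 | 6.6 | 2.49 |
| 12 months | none starts | 15.7 | 3.9 | 4.02 |
| 12 months | 3 months | 11.5 | 3.6 | 3.18 |
| 12 months | 1.5 months | 8.7 | 3.3 | 2.60 |

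The gap runs from 5.4 (8.7 − 3.3) to 28.8 (40.1 − 11.3) per 100 leaving treatment. The only anchor in the documents is a median survival of about one year under combination chemotherapy (Protocol 5.3). That is not survival from last dose, so 12 months is more likely high than low.

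**5. Visit windows.** Using 85 and 26 days, or 95 and 16 days, instead of 90 and 21 widens the range of ratios to 1.98–5.52. The direction does not change.

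**6. Common window.** If both arms are cut at 21 days, equal hazards give equal capture: 3.9% in each arm at a 12-month median and 7.7% at 6 months, with no new therapy. The ratio is 1.

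**7. Crossover.** Crossover dosing starts at least 3 weeks after the last chemotherapy dose (crossover schedule, note 1), so it does not shorten a 21-day window. If post-crossover events were pooled into the control column, that column would gain deaths during crossover treatment as well as deaths up to 90 days after it. The gap would shrink and could reverse. No break-even share of controls can be given, because the documents offer no rate for deaths on crossover treatment.

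**The case against.** **The SAP list is open.** It defers to reporting standards that are not in the documents and is expressly non-exhaustive, so suitable rows may exist there. This stands. The most that can be said is that the SAP's own list names none.

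**Some rows do drop PD deaths.** A reader might infer that no SAE row is free of them. The documents do not support that. The treatment-related and drug-related SAE rows omit PD deaths judged unrelated, and collection of related SAEs has no time limit in either arm. However, those rows filter on causality and not on PD, and an indeterminable or missing causality counts as related.

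**Fatal toxicity can be recovered.** Deaths are listed, and severity of adverse drug reactions is summarized (Protocol 14.4.5). A reader might infer that treatment-related deaths would be hidden, which goes too far. They simply have no named by-arm row, although TEAE and TRAE rows are paired for dose changes and discontinuation.

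**The 21-day limit is not wholly clear.** The control schedule also marks AE collection under cycles 7–16 and cycle 17 onward. Protocol 11.3.2 describes control safety follow-up as starting at day 21. Against this, the synopsis, Protocol 7.1 and SAP 2.1 give a 21-day period, and note 19 of the control schedule ends AE recording with safety follow-up. The figure is best called nominal.

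**Equal hazards after last dose are assumed.** Controls may stop after six recommended cycles without progression, while investigational subjects may continue beyond it (8.3.3). This stands as a limit on any size quoted.

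**Longer follow-up for a PD-1 antibody is deliberate.** Protocol 10.1.6.1 notes that immune-related events may appear months after the last dose. That is a sound reason to keep the full window, but not to leave it as the only basis for comparing the arms.

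**Conclusion.** The point holds as a minor one. Followed as written, the plan compares PD deaths and other unrelated SAEs between arms over unequal post-treatment windows in three named all-cause rows, and its own list gives no all-cause row that corrects for either feature. With equal hazards after last dose, the longer window alone puts more events in the investigational column as long as post-crossover events stay out of the control column. If they are pooled, the direction is open. The 2.4 to 4.0 ratio rests entirely on assumed survival, assumed switching, equal hazards and attribution of every death to PD. It shows that the effect need not be trivial but does not predict the table.

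A reader might infer a threat to the trial's conclusions. The documents do not support that: these summaries are descriptive, carry no decision rule and do not enter the PFS analysis.

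**What to change.** Leave SAE reporting and the full-window rows as they are. In SAP 5.5.2 add, by arm:

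- **(a)** Any TESAE, Any SAE and fatal TEAEs, restricted to onset within 21 days after the last dose of randomized treatment and before new anti-tumor therapy;
- **(b)** the same three rows over the full window, excluding deaths the investigator attributed to PD under Protocol 13.2.3;
- **(c)** TRAEs resulting in death.

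State also that post-crossover events are summarized separately and do not appear in the control column.

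The cost is a short SAP amendment, a few table rows and possibly one flag for PD deaths. No new data are needed, because investigators already make this judgment to apply 13.2.3. There are three drawbacks. Attribution to PD is open-label. The 21-day rows miss late immune-related events. They also align only the period after treatment and leave time on treatment unequal. For these reasons the new rows should stand beside the full-window rows and not replace them.
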